9.2.3 Additional Adverse Event Severity Grading

Vital signs will be graded as follows:

Vital Signs*			
Vital Signs	Mild (Grade 1)	Moderate (Grade 2)	Severe (Grade 3)
Fever (°C) **	37.8-38.4	38.5-38.9	≥ 39.0
Hypertension (systolic) mm Hg	141-150	151-155	>155 or an ER visit or hospitalization for malignant hypertension
Hypertension (diastolic) mm Hg	91-95	96-100	>100 or an ER visit or hospitalization for malignant hypertension
Hypotension (systolic) mm Hg	85-89	80-84	<80 or an ER visit or hospitalization for hypotensive shock
Bradycardia – beats per minute ***	50-54 or >10 bpm less than baseline if baseline <60	45-49 or >15 bpm less than baseline if baseline <60	<45 or >20 BPM or less than baseline if baseline <60 , or an ER visit or hospitalization for arrhythmia
Tachycardia – beats per minute	101-115	116-130	>130 or an ER visit or hospitalization for arrhythmia

* Subjects should be at rest for at least 15 minutes prior to vital sign measurements

** Oral temperature; no recent hot or cold beverages or smoking

*** When resting heart rate is between 60-100 beats per minute. Pulse and Blood Pressure assessed at Visit 1 (Day 1) will be considered baseline. Sinus bradycardia among some healthy subject populations, for example, conditioned athletes maybe acceptable.

Abnormal laboratory findings that will trigger an Adverse Event report will include:

- Hematologic: WBC <3.5 or >13.0 ($10^9/L$), Hemoglobin <11.0 or >18.0 .gm/dL, Platelets <130 or >550 ($10^9/L$)

- Hepatic: SGOT (AST) or SGPT (ALT) > 70.0
- Renal: Creatinine > 133 umol/L, Blood Urea Nitrogen > 30 mg/dL, \geq 1+ proteinuria

Laboratory values that are outside of the normal range, but do not meet protocol defined criteria as adverse events will be evaluated by a clinician for clinical significance, recorded in the source document, and reported as laboratory AEs if clinically significant. Other laboratory parameters not specified in the protocol, but performed as part of the CBC and complete metabolic panel, need to be evaluated by a clinician, recorded in the source document, and reported as laboratory AEs if clinically significant.

Hematology	Mild (Grade 1)	Moderate (Grade 2)	Severe (Grade 3)
WBC 10 ⁹ /L (Decrease)	3.0-3.4	2.0-2.9	<2.0
WBC 10 ⁹ /L (Increase)	13.1-13.9	14.0-15.0	>15.0
Hgb g/dL (Decrease)	9.1-10.9	7.5-9.0	<7.5
Hgb g/dL (Increase)	18.1-18.5	18.6-19.0	>19.0
Platelets 10 ⁹ /L (Decrease)	100-130	50-99	<50
Platelets 10 ⁹ /L (Increase)	551-600	601-700	>700

Chemistry	Mild (Grade 1)	Moderate (Grade 2)	Severe (Grade 3)
BUN mg/dL	31-60	>60- and \leq 70	>70
Creatinine umol/L ¹ (Increase)	134-176	177-221	>221
AST IU/L (Increase)	70.1-200	201-300	>300
ALT IU/L (Increase)	70.1-200	201-300	>300

Urinalysis	Mild (Grade 1)	Moderate (Grade 2)	Severe (Grade 3)
Protein	1+	2+	hospitalization or dialysis

¹Conversion factor from mg/dL: <http://onlinelibrary.wiley.com/doi/10.1002/97808138188825.app3/pdf>

²Trace protein at screening (Visit 00B) is acceptable for inclusion into the study

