6. Vital signs (oral temperature, pulse, and blood pressure) are all within normal protocol-defined ranges (abnormal criteria defined in Section 9.2.3 Additional Adverse Event Severity Grading).
7. Laboratory tests (blood urea nitrogen, creatinine, AST, ALT, white blood cells, platelets, hemoglobin) are all within protocol-defined ranges.

Subjects will be eligible for enrollment with the following laboratory values:

- Blood urea nitrogen less than or equal to 30 mg/dL
 - Creatinine less than or equal to 133umol/L
 - AST or ALT less than or equal to 70.0 U/L
 - White cell count between 3.5 and 13.0 inclusive($10^9/L$)
 - Platelets between 131 and 550 ($10^9/L$) inclusive
 - Hemoglobin between 11.0 and 18.0 gm/dL inclusive
8. Urinalysis with no greater than trace protein. If a high protein is confirmed to be due to menstruation, it should be repeated.
 9. Women of reproductive potential⁴ must have a negative urine pregnancy test within 72 hours of starting study medications.

⁴Female subjects who are surgically sterile via tubal sterilization, bilateral oophorectomy or hysterectomy, who have been postmenopausal for greater than 1 year are not considered to be of reproductive potential.

10. Female subjects participating in sexual activity that could lead to pregnancy must be using and continue to use highly effective⁵ contraception for a total of 4 months after enrollment.

⁵Highly effective methods of contraception are defined as having low failure rates (i.e. less than 1% per year) when used consistently and correctly and may include, but are not limited to, abstinence from intercourse, monogamous relationship with a vasectomized partner, male condoms with spermicide, diaphragm with spermicide, intrauterine devices, and licensed hormonal methods. Females on effective forms of birth control will continue while on the study and for the follow-up period of 4 months total. The method and compliance of birth control used will be confirmed and documented at all study visits.

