8 STUDY PROCEDURES/EVALUATIONS

8.1 Clinical Evaluations

Medical History: Complete medical history will be obtained by interview of the subjects at the screening visit (Visit 00B) and will be reviewed and updated on Day 1 (Visit 01) prior to the first study product administration. Subjects will be queried regarding a history of significant medical disorders of the head, eyes, ears, nose, throat, mouth, cardiovascular system, lungs, gastrointestinal tract, liver, pancreas, kidney, urologic system, nervous system, blood, lymph nodes, endocrine system, musculoskeletal system, skin, and genital/reproductive tract. A history of any allergies, cancer, immunodeficiency, psychiatric illness, substance abuse, and autoimmune disease will be solicited. At follow-up visits after the first dose, an interim medical history will be obtained, when indicated, by interview of the subjects noting any changes since the previous visit.

Concomitant Medications: Concomitant medications will include a review of all current medications and medications taken within 30 days prior to signing the informed consent form and through approximately 30 days after the first study product administration. Prescription and over-the-counter drugs will be included as well as vitamins and supplements. Assessment of eligibility will also include a review of all permitted and prohibited medications per the Subject Inclusion and Exclusion Criteria (see Section 5).

Physical Examination and Vital Signs: A physical examination limited to vital signs (blood pressure, pulse, temperature), observation for rashes or glossitis, and an abdominal exam will be performed at screening (Visit 00B). On Day 1 (Visit 01) prior to the first study product administration and at follow-up visits after the first administration of study product, a targeted physical examination will be performed, if indicated, based on subject's interim medical history.

Adverse Events: Subjects will be interviewed to determine the occurrence of unsolicited AEs.

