Hypertension (diastolic) mm Hg	91-95	96-100	>100 or an ER visit or hospitalization for malignant hypertension
Hypotension (systolic) mm Hg	85-89	80-84	<80 or an ER visit or hospitalization for hypotensive shock
Bradycardia – beats per minute ***	50-54 or >10 bpm less than baseline if baseline < 60	45-49 or >15 bpm less than baseline if baseline < 60	<45 or > 20 BPM or less than baseline if baseline < 60, or an ER visit or hospitalization for arrhythmia
Tachycardia – beats per minute	101-115	116-130	>130 or an ER visit or hospitalization for arrhythmia

* Subjects should be at rest for at least 15 minutes prior to vital sign measurements
 ** Oral temperature; no recent hot or cold beverages or smoking
 *** When resting heart rate is between 60-100 beats per minute. Pulse and Blood Pressure assessed at Visit 1 (Day 1) will be considered baseline. Sinus bradycardia among some healthy subject populations, for example, conditioned athletes maybe acceptable

Table 7: Laboratory Adverse Event Grading Scale

NOTE: For grading ranges that were updated in protocol revisions, all ranges are shown in the below table, with their corresponding protocol versions. No subjects were enrolled under Protocol Versions 1-3, so ranges from those versions are omitted. Events are graded according to the protocol version that was active at the time of the event. Effective dates are: Version 4.0: 18Oct2016, Version 5.0: 12Dec2017, Version 6.0: 07Aug2018, Version 7.0: 23Jul2019

Hematology	Mild (Grade 1)	Moderate (Grade 2)	Severe (Grade 3)
WBC 10 ⁹ /L (Decrease)	Version 4: 3.0-3.9 Versions 5-7: 3.0 – 3.4	2.0-2.9	<2.0
WBC 10 ⁹ /L (Increase)	Version 4: 11.1-13.0 Versions 5-7: 13.1-13.9	Version 4: 13.1-15.0 Versions 5-7: 14.0-15.0	>15.0
Hgb g/dL (Decrease) (Female)	Versions 4-6: 9-11.4 Version 7: 9.1-10.9	7.5-9.0	<7.5
Hgb g/dL (Decrease) (Male)	Versions 4-6: 9-12.4 Version 7: 9.1-10.9	7.5-9.0	<7.5
Hgb g/dL (Increase)	Versions 4-6: N/A Version 7: 18.1-18.5	Versions 4-6: N/A Version 7: 18.6-19.0	Versions 4-6: N/A Version 7: >19.0
Platelets 10 ⁹ /L (Decrease)	Version 4: 100-149 Versions 5-7: 100-130	50-99	<50
Platelets 10 ⁹ /L (Increase)	Version 4: 451-480 Versions 5-7: 551-600	Version 4: 480-500 Versions 5-7: 601-700	Version 4: >500 Versions 5-7: >700

Chemistry	Mild (Grade 1)	Moderate (Grade 2)	Severe (Grade 3)
BUN mg/dL	Version 4: 25-60 Versions 5-7: 31-60	Versions 4-7: 60-70 [†] Version 8: >60 and ≤70	>70

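### Grade 3 bradycardia cell in Protocol 9.2.3 and SAP Table 6 has a stray second *or*: as printed, any fall from a baseline pulse under 60 is severe (minor drafting error)

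*Protocol*

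**What the plan says.** The bradycardia row of the vital-signs table in Protocol 9.2.3 has three cells. Grade 1 is "50-54 or >10 bpm less than baseline if baseline <60". Grade 2 is "45-49 or >15 bpm less than baseline if baseline <60". Grade 3 starts with a pulse below 45, continues ">20 BPM or less than baseline if baseline <60", and ends with emergency or hospital care for arrhythmia. SAP 4.5.1, Table 6, prints the same Grade 3 wording: "> 20 BPM or less than baseline if baseline < 60".

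The footnote to the row takes the Day 1 pulse as baseline. It opens with "When resting heart rate is between 60-100 beats per minute" and closes with "Sinus bradycardia among some healthy subject populations, for example, conditioned athletes maybe acceptable".

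The row is used in several places:

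- **Eligibility.** Inclusion criterion 6 in Protocol 5.1 refers to it ("abnormal criteria defined in Section 9.2.3 Additional Adverse Event Severity Grading").
- **Reporting.** SAP 4.5.1 names Table 6 as the grading for vital signs, and SAP 9.7 tabulates them by visit, severity and treatment group. Tables 67 and 73 (any assessment) and Tables 71 and 77 (bradycardia) take their severity columns from it.
- **Dosing.** Under Protocol 9.4.1, a Grade 3 event judged drug-related ends that subject's dosing and is notified to the DSMB.

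**The concern.** In Grades 1 and 2 the fall from baseline is a single condition with a size and a reference point. In Grade 3 the extra *or* cuts that condition in two. The first half, more than 20 BPM, no longer says what it is measured against. The second half no longer has a size, so it is met by any pulse below a baseline that is itself under 60.

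If the cell is programmed or applied as printed, a change of one beat is reported as severe bradycardia. The shells for the four SAP tables have a row for each visit to Day 28 and a row for the worst grade after baseline, which includes unscheduled assessments. One such reading is therefore enough to put a subject in the severe column. A clinician who followed the printed grade and also judged the event drug-related would have to stop dosing.

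The sponsor has repaired a smaller fault of this kind. SAP Table 7 notes that a BUN of 60 fell into both the mild and the moderate range and states how it will be classified, and the current Protocol 9.2.3 range no longer overlaps. The bradycardia cell did not get the same attention.

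**Working it through.** The documents give no figure to reproduce. The check is a comparison of wording, followed by worked examples.

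**The fall conditions side by side, for a baseline under 60**

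| Grade | Absolute limit | Fall condition as printed | Fall condition that fits the row |
|---|---|---|---|
| 1 | 50-54 | more than 10 bpm below baseline | more than 10 bpm |
| 2 | 45-49 | more than 15 bpm below baseline | more than 15 bpm |
| 3 | below 45 | more than 20 BPM, *or* below baseline | more than 20 bpm |

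Only the Grade 3 cell has an *or* inside its fall condition. The same word stands in both documents, so a fault in reading the PDF is unlikely.

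**Examples, taking the highest grade met.** The last column applies the absolute limits at every baseline.

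| Day 1 to later pulse | Fall (bpm) | As printed | Second *or* deleted |
|---|---|---|---|
| 59 to 58 | 59 - 58 = 1 | Grade 3 | not graded |
| 59 to 52 | 59 - 52 = 7 | Grade 3 | Grade 1 (within 50-54) |
| 59 to 48 | 59 - 48 = 11 | Grade 3 | Grade 2 (within 45-49) |
| 59 to 43 | 59 - 43 = 16 | Grade 3 | Grade 3 (below 45) |

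The first line does not depend on how the footnote is read: 58 is in no absolute band, and a fall of 1 is not more than 10. As printed, Grades 1 and 2 can never be the highest grade for any fall from a baseline under 60, because every such fall already meets Grade 3.

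**The stranded fragment.** Read alone as a pulse value, more than 20 BPM would make almost every reading severe, including a change from 62 to 58 that meets no other condition in the row. The cell therefore cannot be applied word for word, and whoever programs it has to choose a repair.

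**What the correction loses.** From a baseline under 60, a fall of more than 20 bpm leaves a pulse below 60 - 20 = 40, which is already under 45. Where the absolute limit applies, the intended condition adds no severe grades of its own. The printed version adds only wrong ones.

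**Who can be affected.** A subject needs a Day 1 pulse under 60 and a later pulse reading. Protocol Appendix A marks vital signs only at Visits 00B and 01, and Protocol 8.1 says that at follow-up "a targeted physical examination will be performed, if indicated". SAP 4.5.1 and 9.7 say that vital signs are taken at every visit. That would be 7 later readings in giardiasis (Visits 02, 03, 04, 05, 07, 08, 09) and 7 + 1 = 8 in amebiasis, which adds Visit 06.

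**The case against.** The strongest reply is that this is a slip of one word with one workable meaning. The steps of 10 and 15 show that 20 was meant as the next step, and site staff would probably read it that way. Taking the second half of the broken clause literally while setting aside the equally literal first half is a choice, and nothing shows that anyone would make it. A study physician assesses severity and relatedness (Protocol 9.2.1), so a treatment stop for a pulse of 58 is hard to imagine. If Appendix A is followed, there may be no later readings to grade.

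Most of this stands. It fixes the class of the error (drafting) and its size (minor). It does not remove the error. The table is a threshold that gets programmed, the SAP repeats the fault, and neither document says which repair to use.

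The footnote does not rescue the cell. Its opening phrase fits poorly with conditions written for baselines under 60, and its closing sentence allows judgment about low pulses without setting a threshold.

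**Conclusion.** The Grade 3 cell is wrong as written in both documents and should be corrected. The error is minor. It can affect only subjects with a Day 1 pulse under 60 and a reading after baseline. The documents do not give that number, and it may be zero. No efficacy endpoint and none of the study halting rules in Protocol 9.4.1 depends on the grade. The conclusion assumes that the intended condition is a fall of more than 20 bpm, which the row supports and no other text contradicts.

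Four stronger readings are tempting, and the documents do not support them:

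- **That severe bradycardia will be materially over-reported.** Every fall from a low baseline meets the printed condition, but that describes the rule and not the patients. It also rests on applying half of the clause literally.
- **That only Day 1 pulses of 55-59 are exposed, because Grade 1 starts at 54 and inclusion 6 uses this table.** The graded baseline is the Day 1 pulse, while vital signs are also taken at screening Visit 00B and eligibility may rest on that value. The footnote may also admit lower pulses. The cap is not established.
- **That trivial falls will stop dosing.** The stop also needs a judgment that the event is drug-related.
- **That the scope of the footnote is part of this error.** Whether the absolute bands apply to baselines under 60 is a separate question. The second *or* is wrong under either answer.

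**What to change.** In Protocol 9.2.3 and SAP Table 6, delete the *or* between the 20 bpm figure and the reference to baseline. The cell then means: a pulse below 45; or a fall of more than 20 bpm from a baseline under 60; or emergency or hospital care for arrhythmia. Program SAP Tables 67, 71, 73 and 77, and their repeats for the symptomatic population, from the corrected cell.

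The cost is one word in one cell of each document, by clarification letter or with the next amendment and SAP version. It needs no new data, procedures or patients. If the footnote is opened at the same time, one sentence saying whether the absolute bands apply to baselines under 60 would help, but that is optional.

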Severity of Event: AEs will be assessed by a licensed study physician listed on the Form FDA 1572 as the site principal investigator or appropriate sub-investigator using a protocol-defined grading system (see Section 9.2.2 and 9.2.3). For events not included in the protocol-defined grading system, the following guidelines will be used to quantify severity:

- Mild (Grade 1): Events require minimal or no treatment and do not interfere with the subject's daily activities.
- Moderate (Grade 2): Events result in a low level of inconvenience or concern with therapeutic measures. Moderate events may cause some interference with functioning and daily activities.
- Severe (Grade 3): Events that prevent the subject's usual daily activities and may require systemic drug therapy or other treatment. Severe events are usually incapacitating.

The severity of systemic and clinical laboratory adverse events will be graded according to Section 9.2.2 and the toxicity tables included in the Appendices to this protocol.

Changes in the severity of any AE will be documented to allow an assessment of the duration of the event at each level of intensity. When AEs are intermittent, the onset and duration of each episode will be documented.

Relationship to Study Products: The study physician's assessment of an AE's relationship to study product is part of the documentation process, but it is not a factor in determining what is or is not reported in the study. If there is any doubt as to whether a clinical observation is an AE, the event should be reported. The relationship to study product must be assessed for AEs using the terms: related or not related. In a clinical trial, the study product must always be suspect. To help assess, the following guidelines are used:

- Related – There is a reasonable possibility that the study product caused the adverse event. Reasonable possibility means that there is evidence to suggest a causal relationship between the study product and the adverse event.
- Not Related – There is not a reasonable possibility that the administration of the study product caused the event.

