9.4.1. Halting Rules

Individual Halting Rules: Dosing for an individual subject will be discontinued if they develop any grade 3 drug-related event. The DSMB has requested to be notified of any individual subject who experiences a grade 3 drug-related event, however, the study will continue enrollment.

Study Halting Rules: Enrollment, dosing and study procedures will be halted for DSMB review/recommendation if any of the following are reported:

- Any death occurring after administration of study drug through the subject's last study visit that was not the result of trauma or accident, regardless of relatedness to study product.
- Any subject experiences a study drug-related SAE from the time of receipt of study drug through the subject's last study visit after relatedness is finalized by DMID.
- Occurrence of a severe allergic/hypersensitivity reaction (anaphylaxis) within 48 hours of dosing, requiring hemodynamic support with vasoactive medications or mechanical ventilation; the signs/symptoms will include any of the following: bronchospasm, dyspnea, wheezing, stridor, hypoxemia urticaria, angioedema, hives, and facial or oropharyngeal edema.

If any of the halting rules are met following any subject receipt of study drug, the study will not continue with the remaining enrollments without a review by and recommendation from the DSMB to proceed.

DMID retains the authority to suspend additional enrollment and study interventions/administration of study product during the entire study, as applicable.

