In general, analyses will incorporate the modified intent-to-treat (mITT) principle. Participants who are "randomized and receive at least one dose of study medication" will be included in the mITT population. Subjects who terminate their treatment regimen and receive metronidazole due to worsening symptoms will be imputed as treatment failures for the primary outcome. That is, they will be imputed as still symptomatic by Day 7 in the amebiasis group, and by Day 5 in the giardiasis group. Secondary outcomes measured at Days 3, 5, and 7 will be imputed analogously, with the exception of the quantitative trophozoite/cyst load. Multiple imputation may be used to adjust for missing data in the primary and secondary analyses on the mITT population. All results will be reported as point estimates (odds ratios or mean differences across groups, as appropriate) and interval estimates (95% confidence intervals). All tests of significance for the secondary outcomes will be 2-sided and no adjustments will be made for multiple comparisons. A p-value of 0.05 will be considered statistically significant. The Statistical Analysis Plan (SAP) will provide further details. In case the language in this section differs from the language in the SAP, the SAP takes precedence.

In the event that recruitment and follow-up for either the Giardiasis arm or the Amebiasis arm is completed ahead of the other, the primary and secondary endpoints may be analyzed for that arm using the specified methods. This report will be considered the interim CSR and will contain detailed unblinded information about the participants, their immunological response to treatment as well as their side effects and any laboratory abnormalities. The interim CSR will be followed with a release of data corresponding to the report. In order to maintain the blind and allow appropriate follow up of the remaining arm, no endpoint data for the remaining arm will be included in the interim CSR and no data related to that arm will be released. An amendment to the interim CSR will provide primary and secondary analysis of the remaining arm when all primary and secondary endpoint data are available for the second arm. The official reports will be drafted by Emmes and reviewed by the PI and DMID prior to finalization. Additional information regarding the methods will be provided in the study SAP.

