Solicited events are AEs that are known to occur with this study product. Adverse event data is collected at each visit using specific questions and/or targeted physical examination. Based on the adverse reactions listed on the package insert, these include: loose stools or diarrhea, abdominal pain, nausea with or without vomiting, constipation, anorexia, flatulence, dyspepsia, dysgeusia, pruritus, hair loss, urticarial, stomatitis, conjunctivitis, glossitis, hematuria, and rashes. As noted above, diarrhea is considered an adverse event only in the asymptomatic population as it is a condition for enrollment in the symptomatic population. Physical examinations look for abdominal pain, hair loss, urticaria, rashes, stomatitis, conjunctivitis, and glossitis. In the symptomatic population, solicited AEs are not collected that are related to any prescribed metronidazole. Adverse event collection continues until Day 28 (following three half-lives of the drug). Each solicited adverse event described above is graded as Mild (Grade 1) if it “Does not interfere with daily activity”, as Moderate (Grade 2) if it “Interferes with daily activity”, and as Severe (Grade 3) if it “Prevents daily activity (incapacitating)”. Grading for vital signs, also collected on every visit, is given in [Table 6](#). Furthermore, hematology, biochemistry, and urine labs are analyzed on Study Day 7. Grading for these adverse events is given in [Table 7](#). Some laboratory grading ranges were modified in protocol updates; these modifications are displayed in the table. Laboratory results are graded according to the protocol effective on the date the sample was collected. The effective date is the date that the site received IRB approval for the version and began implementing that version. (The effective date is later than the protocol version date, which indicates when the version was approved by DMID.) The first subjects in the study enrolled under Protocol Version 4.0, so laboratory ranges for earlier protocol versions are not displayed. The effective dates are as follows: Version 4.0: 18Oct2016, Version 5.0: 12Dec2017, Version 6.0: 07Aug2018, Version 7.0: 23Jul2019.

Table 6: Vital Signs Grading Scale

Vital Signs*			
Vital Signs	Mild (Grade 1)	Moderate (Grade 2)	Severe (Grade 3)
Fever (°C) **	37.8-38.4	38.5-38.9	>= 39.0
Hypertension (systolic) mm Hg	141-150	151-155	>155 or an ER visit or hospitalization for malignant hypertension

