Creatinine umol/L ¹ (Increase) (Male)	Version 4: 107-176 Versions 5-7: 134-176	177-221	>221
Creatinine umol/L ¹ (Increase) (Female)	Version 4: 98-161 Versions 5-7: 134-176	Version 4: 162-202 Versions 5-7: 177-221	Version 4: >202 Version 5-7: >221
AST IU/L males (Increase)	Version 4: 38.1-200 Version 5: 60.1-200 Versions 6 and 7: 70.1-200	201-300	>300
AST IU/L females (Increase)	Version 4: 32.1-200 Version 5: 60.1-200 Versions 6 and 7: 70.1-200	201-300	>300
ALT IU/L males (Increase)	Version 4: 41.1-200 Version 5: 60.1-200 Versions 6 and 7: 70.1-200	201-300	>300
ALT IU/L females (Increase)	Version 4: 31.1-200 Version 5: 60.1-200 Versions 6 and 7: 70.1-200	201-300	>300

Urinalysis	Mild (Grade 1)	Moderate (Grade 2)	Severe (Grade 3)
Protein	1+	2+	3+ or hospitalization or dialysis

¹Conversion factor from mg/dL: <http://onlinelibrary.wiley.com/doi/10.1002/9780813818825.app3/pdf>

²Trace protein at screening (Visit 00B) is acceptable for inclusion into the study.

[†]Values of 60 fall into both Mild and Moderate categories for protocol versions 4-7 and will be classified as Mild.

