6.6. Interim Analyses and Data Monitoring

There will be no planned interim analyses for efficacy or futility conducted for this study, but the DSMB may modify this during ongoing safety monitoring. The study team will review all adverse events by cumulative reports on a monthly basis. Adverse events will be graded using the protocol defined grading system. The DSMB, established by the study team, will monitor this study.

The DSMB will review the safety data when the study reaches 50% enrollment (i.e. 34 subjects enrolled per parasite group). The DSMB will review safety data after the 68th subject completes visit 8.

Asymptomatic subjects (34) enrolled under Version 1-4 of the protocol will have their data reviewed and clinical database locked for analysis first and a separate report generated. This may be generated before follow-up is completed in the symptomatic study population.

In the event that recruitment and follow-up for either the Giardiasis arm or the Amebiasis arm is completed ahead of the other, the primary and secondary endpoints may be analyzed for that arm using the specified methods. This report will be considered the interim CSR and will contain detailed unblinded information about the participants, their immunological response to treatment as well as their side effects and any laboratory abnormalities. The interim CSR will be followed with a release of data corresponding to the report.

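### Protocol 9.2.3 and SAP Table 7 disagree on Grade 3 urine protein, so a drug-related 3+ dipstick may miss the individual Grade 3 notice to the DSMB

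*Protocol*

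**What the plan says.** The urinalysis row in Protocol 9.2.3 has three entries for protein: 1+ is Grade 1, 2+ is Grade 2, and Grade 3 is "hospitalization or dialysis". SAP Table 7, in section 4.5.1, has the same first two entries, but its Grade 3 is "3+ or hospitalization or dialysis".

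The SAP defers to the protocol on grading in three places. Section 4.5.1 says "Laboratory results are graded according to the protocol effective on the date the sample was collected". The note above Table 7 says "Events are graded according to the protocol version that was active at the time of the event". Section 6.6 says "Adverse events will be graded using the protocol defined grading system".

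Protocol 9.4.1 attaches two actions to Grade 3. The first is "Dosing for an individual subject will be discontinued if they develop any grade 3 drug-related event". The second is that the DSMB has asked to be told of each such event, while enrollment continues. Protocol 9.4.3 adds that the DSMB uses these notices to decide whether to meet ad hoc.

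**The concern.** Two documents that should carry one scale carry two, and the difference falls at the boundary that triggers safety oversight. Proteinuria is a listed reaction to auranofin (Protocol 2.3.1 and 9.1), so this row is not incidental.

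The protocol row is also unlike its neighbours. Every other laboratory row in 9.2.3 has a numeric Grade 3 limit; protein alone has a Grade 3 defined only by an outcome. Inpatient hospitalization is already a criterion for a serious adverse event (Protocol 9.2.4), so the protocol's Grade 3 for protein catches little that serious-event reporting would not catch anyway.

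Two things are at stake: whether a drug-related 3+ result leads to an individual notice to the DSMB, and whether the severity assigned at the site matches the severity the SAP would assign to the same result.

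**Working it through.** No stated figure needs reproducing. The check compares the two rows and asks whether any other text settles the difference.

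**1. The rows side by side**

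| Dipstick | Hospitalization or dialysis? | Protocol 9.2.3 | SAP Table 7 |
|---|---|---|---|
| Trace | No | no grade | no grade |
| 1+ | No | 1 | 1 |
| 2+ | No | 2 | 2 |
| 3+ | No | **no grade** | **3** |
| Any of these | Yes | 3 | 3 |

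Four dipstick levels, each with or without the clinical outcome, give 4 × 2 = 8 combinations. The documents differ in exactly one.

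**2. Which document governs**

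The three SAP statements quoted above point to the protocol. Table 7's own convention is to show every range that changed between protocol versions with its version label. The protein row has no label, so the SAP presents 3+ as the protocol's unchanged cut-off. The protocol supplied does not contain it.

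Protocol 11.4 does say "In case the language in this section differs from the language in the SAP, the SAP takes precedence", but that covers the final analysis plan in 11.4. It does not reach the grading table in 9.2.3.

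**3. Whether the protocol fills the gap elsewhere**

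Protocol 9.2.1 refers to toxicity tables in the appendices. Appendices A to C hold a visit schedule, a laboratory flow sheet and normal ranges, with no toxicity table.

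The same section has a fallback: "For events not included in the protocol-defined grading system, the following guidelines will be used to quantify severity". Urine protein is included in the grading system, so it is unclear whether the fallback applies to a missing level. If it does, it grades on treatment need and interference with daily activities. A symptom-free 3+ result needing little or no treatment would then fit Mild, below the Moderate given to 2+. Neither reading makes such a result Grade 3.

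**4. What the timing allows**

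Urine protein is scheduled at Visit 00B and Day 7 only (Protocol 7.3.6, 8.2.1 and Appendix A). Giardiasis dosing ends on Day 5, so the dipstick comes 7 − 5 = 2 days after the last dose. The last amebiasis dose is on Day 7 itself, and Protocol 6.3 describes the Day 7 laboratory tests as following completion of the study agent. The Grade 3 dosing stop could bear at most on the final amebiasis dose, or on a result from an unscheduled test.

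**5. What happens to a 3+ result regardless of grade**

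Proteinuria of 1+ or more is a reportable adverse event (Protocol 9.2.3). It is followed up (9.2.5), falls within the study team's monthly review (11.3), and can be seen by the DSMB at its scheduled reviews, which are at least annual and at 50% enrollment (9.4.3). What can fail is the individual notice prompted by Grade 3 and relatedness.

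**The case against.** The strongest reply is that this is a one-cell mismatch with limited consequences. Much of that stands, and it rules out several stronger readings that a reader might infer.

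- **That Grade 3 is the only route to stopping an individual's dosing.** It is not. Protocol 5.3.3 separately provides for discontinuation after any laboratory abnormality when continuing is not in the subject's best interest.
- **That a 3+ result would never reach the DSMB.** It remains an adverse event, Protocol 6.3 says Day 7 abnormalities may be reported to the DSMB on request, and scheduled reviews may include laboratory values. The individual, prompt notice is what may be missed, and only for a result judged related.
- **That the final report would certainly show it as Severe.** SAP 9.6 points to Table 7 for laboratory severity, but the SAP also defers to the protocol version in force. The parameter-specific severity shells cover only white cells, hemoglobin, hematocrit and platelets. A urine protein grade could surface in the any-parameter table or the abnormal-results listing.
- **That a 3+ result would be graded Mild.** That is one possible reading of the fallback.
- **That a number of affected subjects can be worked out.** It is tempting to apply the 1% in Protocol 2.3.1 or the 3-9% in 9.1 to the 68 planned auranofin subjects (34 in each of two disease groups). Those are rates for proteinuria of any grade, largely on long-term therapy. The nearest short-exposure evidence, 15 healthy volunteers given 6 mg daily for 7 days, showed no clinically meaningful laboratory trends (Protocol 2.1.2 and 2.3.1).

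Two further cautions stand. The protocol table was read by program, and its Grade 3 cell differs from the SAP's only by the missing leading 3+ alternative, so the source PDF must be checked. The supplied protocol's Grade 2 range for blood urea nitrogen is the one that SAP Table 7 labels Version 8, while the SAP's effective dates cover Versions 4 to 7. The urinalysis rows of those versions are not available here, so it cannot be said that every 3+ result in the trial is affected.

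None of this removes the contradiction. No text in either document says which cell prevails.

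**Conclusion.** The two documents contradict each other on Grade 3 urine protein, and the protocol table leaves 3+ without hospitalization or dialysis ungraded. The defect is confined to that one combination. Its practical effect is on the individual Grade 3 notification to the DSMB for a related event and on agreement between site grading and SAP Table 7. The effect on dosing is slight. The event itself is not lost, and no case count is supportable.

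The conclusion rests on the protocol cell having been extracted correctly, and it applies to the protocol version supplied. If the PDF shows the 3+ alternative in the protocol as well, the point falls away. Otherwise it should be corrected: it is small, but it sits on a safety trigger for a known reaction to the drug.

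**What to change.** 1. Confirm the Grade 3 protein cell of Protocol 9.2.3 in the source PDF.
2. If the difference is real, reconcile that row with SAP Table 7 so that every dipstick level above 2+ has one stated grade in both documents and severity does not fall as the dipstick rises. Which grade 3+ receives is for the sponsor and DSMB to decide.
3. State in SAP Table 7 which protocol versions the protein row applies to, as is already done for rows that changed.
4. Have the SDCC list the 3+ results already collected and pass any judged related to the DSMB. This informs the DSMB without regrading past results, so it does not conflict with the SAP rule of grading by the version in force at collection.

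The cost is one table cell, one version label and a query of stored dipstick results. No new test or visit is needed.
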